5.4 Removal of Subjects from Therapy or Assessment

5.4.1 Discontinuation of Individual Subjects

A subject may withdraw from the study at any time and for any reason. The Investigator may discontinue any subject's participation for any reason, including an AE, safety concerns or failure to comply with the protocol. See Section 6.1.7 for toxicity management criteria. Subjects will be withdrawn from study drug treatment immediately if any one of the following occurs:

[figure not shown]
• Clinically significant abnormal laboratory result(s) or AE(s), which rule out continuation of the study drug, as determined by the Investigator or the AbbVie TA MD.

- Serious infections (e.g., sepsis) which cannot be adequately controlled within 2 weeks by anti-infective treatment or would put the subject at risk for continued participation in the trial as determined by the Investigator.
- The Investigator believes it is in the best interest of the subject.
- The subject requests withdrawal from study drug or the study.
- Inclusion and exclusion criteria violation was noted after the subject started study drug, when continuation of the study drug would place the subject at risk as determined by the AbbVie TA MD.
- Introduction of prohibited medications or dosages when continuation of the study drug would place the subject at risk as determined by the AbbVie TA MD.
- Subject is non-compliant with TB prophylaxis (if applicable) or develops active TB at any time during the study.
- The subject becomes pregnant while on study drug.
- Malignancy, except for localized NMSC or carcinoma in-situ of the cervix.
- Subjects with disease progression or not responding to treatment are to be withdrawn from study drug treatment based on investigator's discretion.
- Starting at Week 36, subjects who fail to show at least 20% improvement in either or both TJC and SJC compared to baseline at 2 consecutive visits will be discontinued from study drug treatment.
- The subject experiences a serious hypersensitivity reaction without an alternative etiology
- The investigator determines the subject is significantly non-compliant with study procedure(s)

Subjects will have upadacitinib study drug treatment discontinued immediately if any of the following occur:

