6.1.1.3 Adverse Events of Special Interest

The following adverse events of special interest (AESI) will be monitored during the study (see detailed toxicity management in Section 6.1.7):

- Serious infections;
- Opportunistic infections;
- Malignancy (all types);
- Hepatic disorder;
- Adjudicated gastrointestinal perforations;
- Anemia;
- Neutropenia;
- Lymphopenia;
- Herpes Zoster;
- Creatine Phosphokinase (CPK elevation);
- Renal dysfunction;

ABT-494
M15-572 Protocol Amendment 8
EudraCT 2016-004130-24

- Active tuberculosis;
- Adjudicated cardiovascular events (e.g., major adverse cardiovascular event [MACE]);
- Adjudicated embolic and thrombotic events (non-cardiac, non-CNS).
- Bone fracture
- Retinal detachment

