6.1.6 Pregnancy

Pregnancy in a study subject must be reported to AbbVie within 24 hours after the site becomes aware of the pregnancy. Subjects who become pregnant during the study must be discontinued from study drug treatment (Section 5.4.1).

Information regarding a pregnancy occurrence in a study subject and the outcome of the pregnancy will be collected. Pregnancies in study subjects and female partners of male subjects will be collected from the date of the first dose through 30 days of the last dose of oral study drug and 150 days following the last dose of subcutaneous study drug.

Pregnancy in a study subject is not considered an AE. The medical outcome for either mother or infant, meeting any serious criteria including an elective or spontaneous abortion is considered a SAE and must be reported to AbbVie within 24 hours of the site becoming aware of the event.

[figure not shown]
Female subjects should avoid pregnancy throughout the course of the study, starting with the Screening Visit through 150 days after the last subcutaneous study drug administration for female subjects and through 30 days after the last oral study drug administration. Results of a positive pregnancy test or confirmation of a pregnancy will be assessed starting with the Screening Visit through the final study visit.

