Malignancy: Subjects who develop malignancy other than NMSC or carcinoma in-situ of the cervix must be discontinued from study drug. Information including histopathological results should be queried for the confirmation of the diagnosis. Periodic skin examination is recommended for subjects who are at increased risk for skin cancer. Subjects who develop malignancies should be referred to appropriate specialists and managed as per standard of care.

Muscle-related symptoms: If a subject experiences symptoms suggestive of myositis or rhabdomyolysis, consider checking CPK and aldolase with clinical management and/or study drug interruption as deemed appropriate by the treating physician.

ABT-494
M15-572 Protocol Amendment 8
EudraCT 2016-004130-24

Thrombosis Events: Subjects should be assessed for symptoms of thrombosis during the assessment of adverse events. Subjects who develop symptoms of thrombosis should be promptly evaluated and treated appropriately. If the diagnosis of deep vein thrombosis, pulmonary embolus, or non-cardiac, non-neurologic arterial thrombosis is confirmed, subjects taking upadacitinib must be discontinued from study drug.

COVID-19: Interrupt study drug in subjects with a confirmed diagnosis of COVID-19. Consider interrupting study drug in subjects who show signs and/or symptoms with suspicion of COVID-19. Study drug may be restarted if fever is resolved without use of antipyretics for 24 hours and other symptoms improved, or if 5 days have passed since the COVID-19 positive test result (whichever comes last). The COVID-19 eCRF must be completed.

ECG Abnormality: Subjects taking upadacitinib must be discontinued from study drug for a new ECG change considered clinically significant and with a reasonable possibility of relationship to study drug.

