7.0 Protocol Deviations

AbbVie does not allow intentional/prospective deviations from the protocol unless when necessary to eliminate an immediate hazard to study subjects. The principal investigator is responsible for complying with all protocol requirements, and applicable global and local laws regarding protocol deviations. If a protocol deviation occurs (or is identified) after a subject has been enrolled, the principal investigator is responsible for notifying Independent Ethics Committee (IEC)/Independent Review Board (IRB) regulatory authorities (as applicable), and the following AbbVie Clinical Monitor(s):

Primary Contact:

AbbVie Inc.
[name]
[name]
United States of America

Office:

Email:

AbbVie s.r.l.
[name]
United States of America

Office:
Email:

Such contact must be made as soon as possible to permit a review by AbbVie to determine the impact of the deviation on the subject and/or the study.

Examples of protocol deviations include the following:

[figure not shown]
- Subject entered into the study even though she/he did not satisfy entry criteria;
- Subject who developed withdrawal criteria during the study and was not withdrawn;
- Subject who received wrong treatment or incorrect dose;
- Subject who received excluded or prohibited concomitant treatment.

In Japan, the Investigator will record all protocol deviations in the appropriate medical records at site.

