Appendix F. Statistical Analysis to Account for the Impact of COVID-19 Pandemic

This section presents the changes in statistical analysis to handle the missing data due to COVID-19 and the additional data collected related to COVID-19. The Week 24 primary database lock was completed in Jan 2020. The analyses specified in this section only applies to the long-term database lock.

Patient Disposition

Reasons for premature discontinuation of study drug/study will be updated to add two additional reasons related to COVID-19.

[figure not shown]
- COVID-19 Infection
- COVID-19 Logistical restrictions

The number and percentage of subjects who prematurely discontinued from study drug/study due to COVID-19 infection or COVID-19 logistical restrictions will be summarized by randomized treatment group.

Summary of COVID-19 Impacted Visits

Types of missing visits related to COVID-19 will be collected for the protocol prespecified visits. For each visit, the number and percentage of subjects impacted by COVID-19 will be summarized by the types of visit for each randomized treatment group as well as overall:

- In person, partial assessments done
- Virtual visit
- Missed visit

Efficacy Analyses

With respect to COVID-19 pandemic, it would be reasonable to assume that missed visits and missing data due to self-quarantine or local government restrictions on travel or limitations on healthcare resources will impact subjects across treatment arms in a similar fashion and adopt the Missing at Random (MAR) assumption for missing data handling.

As described in Section 9.3, longitudinal analysis models MMRM and GLMM, as well as NRI analysis for binary variables will be used for long term efficacy analysis for the treatment sequences, and will be maintained for long term efficacy analysis in the presence of missing data due to COVID-19.

Additionally, treatment comparisons between each upadacitinib dose versus adalimumab will be made for non-radiographic efficacy endpoints for the originally randomized upadacitinib groups and adalimumab group.

For radiographic related endpoints, the analysis will be based on linear extrapolation imputation (Week 24 and Week 56 analysis) and AO data. MMRM will be used for continuous radiographic endpoints for Week 104 and future analysis.

Safety Analyses

COVID-19 related AEs occurring on or after February 1, 2020 and COVID-19 related deaths occurring on or after February 1, 2020 will be collected.

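### The malignancy stopping rule in Protocol Section 6.1.7 exempts all non-melanoma skin cancer, while Section 5.4.1 exempts only localized disease

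*Protocol*

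**What the plan says.** Two current sections of Protocol Amendment 8 state when a malignancy ends study drug treatment.

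- **Section 5.4.1 (Discontinuation of Individual Subjects)** opens its list with "Subjects will be withdrawn from study drug treatment immediately if any one of the following occurs". One entry is "Malignancy, except for localized NMSC or carcinoma in-situ of the cervix". The list applies to both study drugs.
- **Section 6.1.7 (Toxicity Management), malignancy paragraph**, says: "Subjects who develop malignancy other than NMSC or carcinoma in-situ of the cervix must be discontinued from study drug". The rest of that paragraph covers histopathology, skin examination and specialist referral. None of it limits the NMSC exemption.

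The abbreviation list (Section 1.3) expands NMSC as non-melanoma skin cancer, with no restriction to localized disease.

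The cross-references run mostly one way. Section 5.4.1 tells the reader: "See Section 6.1.7 for toxicity management criteria". Section 6.1.1.3, which lists malignancy of all types as an AESI, also refers to 6.1.7 for detailed management. The malignancy paragraph in 6.1.7 does not refer back to 5.4.1. The pregnancy stopping rule in Section 6.1.6, by contrast, does. No section states an order of precedence.

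**The concern.** A mandatory safety stop is written in two places with different scope, and the looser wording is in the section to which sites are sent when they manage an AESI. A site that goes from the AESI list straight to 6.1.7 reads an unqualified exemption for NMSC. It could then keep a subject with locally advanced or metastatic NMSC on upadacitinib or adalimumab, although 5.4.1 requires immediate withdrawal.

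The issue is the safety of that subject. There is also a compliance consequence, because Section 7.0 gives this as an example of a protocol deviation: "Subject who developed withdrawal criteria during the study and was not withdrawn". The protocol's own risk section (3.2) says that an increased malignancy risk relative to TNF blockers cannot be fully excluded for this drug class, so the rule should be unambiguous.

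**Working it through.** The discrepancy itself involves no arithmetic. Applying the two rules case by case gives:

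| Event on study | Section 5.4.1 | Section 6.1.7 | Agree? |
|---|---|---|---|
| Localized NMSC | exempt | exempt | yes |
| Carcinoma in situ of the cervix | exempt | exempt | yes |
| Any other malignancy that is not NMSC | stop | stop | yes |
| Non-localized NMSC | stop | exempt | **no** |

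The sections differ in one case only, and 6.1.7 is the looser one.

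**Is the difference deliberate?** The other stopping rules stated in both sections can be compared in the same way:

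- gastrointestinal perforation (same exception for appendicitis and mechanical injury);
- myocardial infarction or stroke;
- confirmed venous or non-cardiac, non-neurologic arterial thrombosis;
- a related, clinically significant ECG change;
- congestive heart failure on adalimumab;
- active tuberculosis.

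Each of these agrees on the triggering event. Among the rules compared, malignancy alone carries a different exemption, which points to a drafting slip.

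**Does it reach the analysis?** Malignancy AESIs are identified by MedDRA queries (SAP Section 10.2.1.6, Table 11), with NMSC and malignancy excluding NMSC as separate categories. Neither stopping rule enters those definitions, and neither enters any efficacy test, power figure or alpha allocation.

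**How long can the text still matter?** The inputs are:

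- SAP Appendix F: "The Week 24 primary database lock was completed in Jan 2020". The day is not given, so the whole month is used.
- SAP Section 4.4: the Week 24 analysis follows the last subject's Week 24 visit.
- Protocol synopsis date: 20 December 2023.
- Last main-study visit: Week 260.

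Assume that every subject had completed Week 24 or discontinued by the lock. Then:

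- Weeks from Week 24 to Week 260: 260 − 24 = 236 weeks = 1,652 days.
- 1 January 2020 + 1,652 days = 10 July 2024.
- 31 January 2020 + 1,652 days = 9 August 2024.
- 20 December 2023 to 10 July 2024: 203 days, and 203 / 7 = 29.0 weeks.
- 20 December 2023 to 9 August 2024: 233 days, and 233 / 7 = 33.3 weeks.

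These are upper limits for the last subject. The 7-day visit window is ignored, and site approval of Amendment 8 would come after the synopsis date. Upadacitinib may continue beyond Week 260 under the continued-treatment arrangement in Appendix I, which does not restate the malignancy rule.

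**The case against.** The best counter-argument is that nothing here conflicts. Section 5.4.1 is mandatory on any single criterion, and non-localized NMSC meets one. Section 6.1.7 gives no permission to continue. When two mandatory rules can both be met, the stricter one binds without a precedence clause, and Section 7.0 makes the principal investigator responsible for all protocol requirements. A reader who follows the pointer in 5.4.1 has already been in the section with the stricter rule. The problem therefore arises only for someone who reaches 6.1.7 another way and does not consult the section on stopping drug.

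Other text also makes unexamined continuation unlikely. Section 5.4.1 requires withdrawal for adverse events that preclude further dosing and when the investigator judges it to be in the subject's interest. Section 3.2 asks the investigator to weigh continued upadacitinib in subjects with malignancy risk factors, including current malignancy. Section 6.1.7 itself calls for histopathology and specialist referral. With so little treatment time left, a correction has limited practical value.

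Much of this stands. The stricter rule does bind, the number affected is small, and the remaining time is short. But the added safeguards rest largely on judgment, whereas the rule in 5.4.1 is automatic, and none of them supplies the missing word. The AESI section does send sites directly to 6.1.7. These points limit the severity but do not remove the discrepancy.

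**Conclusion.** The point holds as a minor drafting error in an operative safety rule. Section 6.1.7 omits a stop that Section 5.4.1 requires, in exactly one situation: non-localized NMSC. This rests on a direct reading of two current sentences. The reading of NMSC as covering all non-melanoma skin cancer rests on the abbreviation list and on the absence of any narrower definition.

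The number of subjects affected cannot be derived from the documents and should be small. The limit of 29.0 to 33.3 weeks depends on the assumption about Week 24 completion by the January 2020 lock, and it excludes continued treatment under Appendix I. The gain from correcting the text is a small one in subject safety and protocol clarity.

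**What to change.** In the malignancy paragraph of Section 6.1.7, insert 'localized' before NMSC so that the exemption matches Section 5.4.1. This adopts the sponsor's own stricter wording.

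The cost is one word in one section, at the next amendment or administrative change. Data already collected and all planned analyses are unaffected.

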- 9. Receipt of any live vaccine within 4 weeks (8 weeks in Japan) prior to the Baseline Visit, or expected need of live vaccination during study participation including at least 4 weeks (8 weeks in Japan) after the last dose of oral study drug, and including at least 70 days after the last dose of subcutaneous study drug.
- 10. Subject has received oral or parenteral Traditional Chinese Medicines within 4 weeks prior to Baseline, has received opioid analgesics (except for tramadol or combination of acetaminophen and codeine or hydrocodone which are allowed)

- within 1 week prior to Baseline, or use of inhaled marijuana within 2 weeks prior to Baseline.
- 11. History of an allergic reaction or significant sensitivity to constituents of the study drugs (including adalimumab or its excipients) and/or other products in the same class.
- 12. History of fibromyalgia, any arthritis with onset prior to age 17 years or current diagnosis of inflammatory joint disease other than PsA (including, but not limited to rheumatoid arthritis, gout, overlap connective tissue diseases, scleroderma, polymyositis, dermatomyositis, systemic lupus erythematosus.) Prior history of reactive arthritis or axial spondyloarthritis including ankylosing spondylitis and non-radiographic axial spondyloarthritis is permitted if documentation of change in diagnosis to PsA or additional diagnosis of PsA is made. Prior history of fibromyalgia is permitted if documentation of change in diagnosis to PsA or documentation that the diagnosis of fibromyalgia was made incorrectly.
- 13. History of clinically significant (per Investigator's judgment) drug or alcohol abuse within the last 6 months preceding the Baseline Visit.
- 14. Female subject who is pregnant, breastfeeding or is considering becoming pregnant during the study within 150 days after the last dose of subcutaneous study drug, and within 30 days after the last dose of oral study drug.
- 15. Laboratory values meeting the following criteria within the Screening period:
 - Serum aspartate transaminase (AST) $> 2 \times ULN$;
 - Serum alanine transaminase (ALT) $> 2 \times ULN$;
 - Estimated glomerular filtration rate (GFR) by simplified 4-variable Modification of Diet in Renal Disease (MDRD) formula
 40 mL/min/1.73 m²;
 - Total white blood cell count (WBC) < 2,500/μL;
 - Absolute neutrophil count (ANC) $< 1,500/\mu L;$
 - Platelet count $< 100,000/\mu L$;
 - Absolute lymphocyte count < 800/μL;

- Hemoglobin < 10 g/dL.

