Management of Select Laboratory Abnormalities: For any given laboratory abnormality, the Investigator should assess the subject, apply the standard of care for medical evaluation and treatment following any local guidelines. Specific toxicity management guidelines for abnormal laboratory values are described in Table 4 and may require an appropriate supplemental eCRF be completed. For subjects with ongoing laboratory abnormalities which require data entry into an eCRF, an additional eCRF related to subsequent laboratory abnormalities is only required if the subject has relevant changes in history (e.g., new onset signs or symptoms) or laboratory values which have returned to normal reference range or its Baseline value followed by subsequent laboratory abnormalities meeting toxicity guidelines (considered a new event). All abnormal laboratory tests that are considered clinically significant by the Investigator will be followed to a satisfactory resolution. If a repeat test is required per Table 4, the repeat testing must occur as soon as possible.

[figure not shown]
[figure not shown]

Table 4. Specific Toxicity Management Guidelines for Abnormal Laboratory Values

Laboratory Parameter	Toxicity Management Guideline
Hemoglobin	 If hemoglobin < 8 g/dL interrupt study drug dosing and confirm by repeat testing with a new sample. If hemoglobin decreases ≥ 3.0 g/dL from Baseline without an alternative etiology, interrupt study drug dosing and confirm by repeat testing with new sample. If hemoglobin decreases ≥ 3.0 g/dL from Baseline and an alternative etiology is known or the hemoglobin value remains in the normal reference range, the subject may remain on study drug at the investigator's discretion. If confirmed, continue to withhold study drug until hemoglobin value returns to normal reference range or its Baseline value.
Absolute neutrophil count (ANC)	 If confirmed < 1000/μL by repeat testing with new sample, interrupt study drug dosing until ANC value returns to normal reference range or its Baseline value. Interrupt study drug if confirmed < 500/μL by repeat testing with new sample. If value returns to normal reference range or its Baseline value, restarting study drug is allowed if there is an alternative etiology identified; documentation should include reason that rechallenge is expected to be safe for the subject. Study drug should be discontinued if no alternative etiology can be found.

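### Table 4 gives two answers for a hemoglobin below 8 g/dL after a fall of at least 3.0 g/dL with a known other cause, and states no precedence

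*Protocol*

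**What the plan says.** The hemoglobin row of Table 4 (Protocol Section 6.1.7) holds three triggers and a closing sentence. They are numbered here for reference.

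- Rule 1, absolute level: "If hemoglobin < 8 g/dL interrupt study drug dosing and confirm by repeat testing with a new sample".
- Rule 2, unexplained fall: "If hemoglobin decreases ≥ 3.0 g/dL from Baseline without an alternative etiology, interrupt study drug dosing and confirm by repeat testing with new sample".
- Rule 3, fall that is explained or still in range: "If hemoglobin decreases ≥ 3.0 g/dL from Baseline and an alternative etiology is known or the hemoglobin value remains in the normal reference range", then "the subject may remain on study drug at the investigator's discretion".
- Closing sentence: "If confirmed, continue to withhold study drug until hemoglobin value returns to normal reference range or its Baseline value".

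Rule 1 has no condition on cause. Rule 3 has no lower limit on the value. Nothing in the row ranks the rules or marks one as an exception to another.

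The entry criterion in Section 5.2.2 excludes "Hemoglobin < 10 g/dL" during Screening. Anemia is an adverse event of special interest (Section 6.1.1.3). Section 3.2 names reduced hemoglobin among the laboratory changes seen with upadacitinib, and Section 5.6.4 cites hemoglobin as a consideration in choosing the doses.

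**The concern.** A toxicity rule should give one action for each set of findings. Here one set of findings leads to two. A site that interrupts a subject at 7.5 g/dL with a documented cause can cite rule 1. A site that continues dosing the same subject can cite rule 3. Monitors have no text by which to call either one a deviation.

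What is at stake is consistent handling of a listed event of special interest while treatment continues in the long-term extension. One literal reading permits dosing below the row's own interruption threshold.

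The other two gaps are smaller. An unexplained fall that leaves the value in the normal range meets rule 2 (interrupt) and also rule 3 (may continue), and the text does not say that rule 3 qualifies rule 2. The closing sentence comes directly after the permissive rule, so its trigger has to be guessed.

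**Working it through.** The documents give no figure to reproduce on this point. The check is one of logic.

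**Inputs.** Let b be the Baseline hemoglobin, h the on-study value and d = b − h, all in g/dL. Table 4 supplies the thresholds 8 and 3.0. Section 5.2.2 supplies the entry floor of 10, which applies at Screening, so Baseline is taken as about 10 or more. The documents give no reference range. Lower limits of 12.0, 13.0 and 13.5 are assumed where one is needed.

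**Conditions.**
- Rule 1: h < 8 → interrupt.
- Rule 2: d ≥ 3.0 and no alternative cause → interrupt.
- Rule 3: d ≥ 3.0 and (alternative cause known, or h in the normal range) → may continue.

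**Rules 1 and 3 together.** Both hold when h < 8, d ≥ 3.0 and another cause is known. No reference range is needed.
- If b ≥ 11.0 and h < 8, then d > 11.0 − 8.0 = 3.0. The fall criterion is always met.
- Example: 12.0 → 7.5, d = 4.5, cause known. Rule 1 says interrupt, rule 3 says may continue.
- Example near the boundary: 11.0 → 7.9, d = 3.1. Both apply.
- With values recorded to 0.1, the same holds from b = 10.9 (10.9 − 7.9 = 3.0).
- For b from 10.0 to 10.8, some values below 8 fall short of 3.0. Example: 10.0 → 7.1, d = 2.9, so only rule 1 applies. A deeper fall brings rule 3 in: 10.0 → 7.0, d = 3.0.

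A grid check used b from 10.0 to 18.0 (81 values) and h from 5.0 to 7.9 (30 values) in steps of 0.1, with the cause known. Of 81 × 30 = 2,430 combinations, 2,385 meet both rules and 45 meet rule 1 only. These are grid cells, not subjects, and say nothing about frequency.

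**Rules 2 and 3 together.** Both hold when d ≥ 3.0, no other cause is found and h is at or above the lower limit of normal (LLN). This needs b ≥ LLN + 3.0.

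| Assumed LLN | Smallest Baseline |
|---|---|
| 12.0 | 15.0 |
| 13.0 | 16.0 |
| 13.5 | 16.5 |

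Example: 16.5 → 13.5, d = 3.0, in range at all three limits.

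**Does other text settle it?** The paragraph before Table 4 asks the investigator to assess the subject and follow standard of care. Section 5.4.1 withdraws subjects for clinically significant laboratory results that rule out continuation. Neither ranks the hemoglobin rules.

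**Other rows.** The relative creatinine trigger also requires a value above the upper limit of normal, so an in-range value cannot set it off. The two CPK actions are separated by the presence or absence of symptoms. Neither row has this kind of overlap.

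**The case against.** The strongest reply starts from the wording of rule 3. When another cause is known, its first limb is enough. The normal-range limb therefore does separate work only for subjects with no known cause, and these are the rule 2 subjects. Unless rule 3 qualifies rule 2, that limb has no function. This is persuasive, and it is the better reading of the second overlap. What stands against the text there is only that the exception is not stated.

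A reader might go further and infer that the closing sentence creates a hold with no duration, because an in-range subject already meets the condition for resuming. The documents do not support that. If rule 3 excepts in-range subjects from rule 2, they need not be interrupted and the problem does not arise.

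For the conflict below 8 g/dL, the reply is that rule 3 repeats the fall criterion, never mentions 8 g/dL and is permissive, while rule 1 is mandatory. A site that interrupts satisfies both. Rule 3 may also sit under the fall criterion in the formatted table, since nesting cannot be judged from the wording alone. These are fair inferences, but they remain inferences. Rule 1 has no condition on cause, rule 3 has no floor, and no sentence says that discretion under one leaves the other intact.

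Investigator judgment and standard of care are real safeguards for the individual subject. They do not make sites act alike.

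**Conclusion.** The row is wrong as written for one defined group: value below 8 g/dL, fall of at least 3.0 g/dL from Baseline, and a known alternative cause. For that group the literal text both requires interruption and permits continued dosing. The conclusion uses only the thresholds in Table 4. For Baselines of 11.0 g/dL or more, the fall condition adds no restriction once the value is below 8.

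The missing exception wording between rules 2 and 3, and the unassigned closing sentence, are secondary drafting gaps.

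Two stronger readings are tempting and should not be drawn. The first is that most eligible subjects are affected, because the entry floor is 10 g/dL. The documents give no Baseline hemoglobin distribution, and a Baseline that makes the conflict possible is not the same as a subject who meets it. The second is that non-responder imputation carries the inconsistency into the efficacy results, since long interruptions become discontinuations (Section 5.5.4). Nothing quantifies this, and SAP Section 11.1 states that the primary efficacy analysis and Period 1 reporting are complete. The supported consequence is uneven safety management between sites in ongoing treatment.

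**What to change.** The sponsor should reconcile the hemoglobin rules in this row of Table 4 so that each set of findings leads to one action. The revised text should state:

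1. which rule takes precedence when both the below-8 g/dL rule and the rule permitting continued dosing are met;
2. whether the third rule is an exception to the second;
3. which triggers the closing sentence on continued withholding governs.

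The choice of rule belongs to the medical team, and none is proposed here. The cost is rewording one table row, with no new procedures, visits or data collection.
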